4.0 Study Design

4.1 Describe and explain the study design (e.g. case-control, cross-sectional, experimental, interventional, longitudinal, and observational). Indicate if there is randomization, blinding, control group, etc. If randomizing, explain how this will be achieved. For studies that have a complex study design (i.e., multiple arms and treatments), include a schematic diagram.

This study will have a pilot phase and a randomized phase. The pilot phase will include 1-3 subjects who will receive real rTMS and rehabilitation. Subjects in the placebo controlled randomize phase will receive rehabilitation combined with either real or sham rTMS. Randomization will be performed in REDCap and be stratified by upper or lower extremity. Randomization will occur in blocks of 4 to ensure equal distribution. Patients and the physical therapists delivering rehabilitation will be blinded to group allocation (real/sham rTMS). The researcher administering the rTMS will not be blinded.

Changes included in protocol version 2:

- Addition of new advertisement document that will be handed out by clinicians to potential subjects.
- Addition of a pilot phase that will include 1-3 unrandomized subjects.
- Adjusted the subject numbers to reflect the pilot phase subjects.
- Added [name] to the study team.
- Created new informed consent document for the pilot phase.

5.0 Data Management and Analysis

5.1 Describe the data analysis plan, including any statistical procedures. This section applies to both quantitative and qualitative analysis

- 1) Primary: NPRS weekly average: 2-way ANOVA for within and between effects.

Secondary:

- 2) NPRS worse/least 24 hours: 2-way ANOVA for within and between effects.
- 3) NPRS number reaching 30% improvement: Descriptive (%), Logistic Regression
- 4) PROMIS: 2-way ANOVA for within and between effects.
 - a. Pain interference
 - b. Pain behavior
 - c. Physical functioning

- d. Satisfaction with discretionary social activity
 - e. Satisfaction with social roles
 - f. Fatigue
 - g. Depression
 - h. Anxiety
 - i. Anger
- 5) GROC: 2-way ANOVA for within and between effects.
 - 6) GROCi: 2-way ANOVA for within and between effects.
 - 7) PASS: Logistic Regression
 - 8) Grip Strength: 2-way ANOVA for within and between effects.
 - 9) 1 Repetition Max Leg Press: 2-way ANOVA for within and between effects.

5.2 *If applicable, provide a power analysis for the number of subjects to be included. If qualitative research, so state, and provide general justification for the total number of subjects proposed.*

NOTE: This may not apply to certain types of studies, including chart/records reviews, survey studies, or observational studies. This question is asked to elicit whether the investigator has an adequate sample size to achieve the study objectives and justify a conclusion.

The pain numeric rating scale (NPRS) MCID ranges from 1 to 2.5 in the literature. Salaffi et al (2003) found that a reduction of 2.0 points was associated with a rating of “much better” for patients with chronic pain. A review of the literature looking at pain ratings for patients with CRPS showed standard deviations approximately 1.0 to 2.0. Effect size was calculated using a 2-point NPRS change and a standard deviation of 1.7. G*Power 3.1.9.7 was used to calculate the sample size based on a repeated measures ANOVA with between and within measures comparisons. A partial η^2 of .07 (moderate effect size) gave an effect size of .274, $\alpha=0.05$, and power was set at 80%. Sample size was calculated for 2 groups, 4 measurements, with a correlation of .5, and nonsphericity of 1. This resulted in a group size of 10 participants for a total of 20 subjects. To account for dropouts up to 36 subjects will be enrolled in this study.

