1.0 Objectives

1.1 Describe the purpose, specific aims, or objectives of this research. Specifically, explain why it is important to do the study.

The purpose of this study is to investigate the effectiveness of rTMS combined with rehabilitation in patients with complex regional pain syndrome type 1 (CRPS). CRPS is associated with pain, disability, psychological distress, and social interference.^{1,2} The disorder is difficult to treat and often leads to long-term problems. Several interventions are recommended including medication, rehabilitation, cognitive/psychological interventions, and invasive pain management devices such as dorsal column root stimulators.³ Despite these interventions, many individuals have persistent pain and disability. Recent studies have investigated rTMS as an intervention for painful conditions that have a poor response to other treatments.^{4,5} These studies suggest that rTMS leads to reduced pain in the short-term. Three studies have used rTMS to treat patients with CRPS with promising short-term results.⁵⁻⁷ There have been no studies looking at the impact of combining rTMS with high-quality rehabilitation. Combining rTMS and high-quality rehabilitation may lead to better short-term and long-term outcomes. The aims of this study are:

1: Determine the short-term effects of rTMS and rehabilitation on pain intensity, pain interference, physical function, fatigue, depression, anxiety, and satisfaction with participation in social roles.

2: Determine the long-term effects of rTMS and rehabilitation on pain intensity, pain interference, physical function, fatigue, depression, anxiety, and satisfaction with participation in social roles.

2. Prasad, MD A, Chakravarthy, MD K. Review of complex regional pain syndrome and the role of

the neuroimmune axis. *Mol Pain*. 2021;17. doi:10.1177/17448069211006617

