2.0 Scientific/Safety Endpoints

2.1 *Describe the scientific endpoint(s), the main result or occurrence under study.*

NOTE: Scientific endpoints are outcomes defined before the study begins to determine whether the objectives of the study have been met and to draw conclusions from the data. Include primary and secondary endpoints. Some example endpoints are: reduction of symptoms, improvement in quality of life, or survival. Your response should not be a date.

Endpoints:

- 1- The pilot stage of the project will be complete after 12 subjects or 4 months, whichever comes first. At this point, adjustments will be made to the protocol and recruitment strategies as needed. Any changes will be submitted to the IRB for approval.
- 2- Stage two of the study will continue until a total of 20 subjects have completed the testing, or 30 total subjects have been enrolled. If 30 subjects have been enrolled, but less

than 20 subjects have completed the protocol the authors will re-assess the study methods and consider amending the IRB protocol to include more than 30 subjects.

- 3- The study may be stopped if there is no new enrollment in the study for up to 6-months.
- 4- The study will be stopped after the pilot stage if more than 30% of subjects withdraw from the study due to side effects or excessive burden from the treatment protocol.

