6.0 Local Number of Subjects

6.1 *Indicate the total number of subjects who will be enrolled or records that will be reviewed through Upstate.*

Based on the power analysis and overage for dropouts a maximum of 33 subjects will be enrolled in the study. The goal is to have at least 20 subjects complete all testing.

6.2 *If applicable, indicate your screen failure rate, i.e., how many subjects you expect to screen to reach your target sample.*

We are attempting to keep the inclusion/exclusion criterion broad and we are including patients with upper and lower extremity symptoms. After phase one of this project, we will have a better idea of the screening failure rate. Given the lack of alternative treatments for this condition and the impact symptoms can have on quality of life, we feel that potential subjects will be highly motivated to be involved in the study.

6.3 Justify the feasibility of recruiting the proposed number of eligible subjects within the anticipated recruitment period. For example, how many potential subjects do you have access to? What percentage of those potential subjects do you need to recruit?

Recruitment for this study may be challenging due to the rarity of the condition. We are partnered with the Upstate PM&R department who routinely see patients with this condition. We will also send recruitment materials to pain management specialists and surgeons inside and outside the Upstate system.

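### The primary ANOVA names no deciding term or time levels; the test that fits N=20 does not measure either aim's arm difference, and one baseline-adjusted contrast would

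*Combined protocol and SAP*

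**What the plan says.** Section 5.1 specifies the primary analysis in one line: "Primary: NPRS weekly average: 2-way ANOVA for within and between effects". No deciding term, time levels, contrast or covariate is given.

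The aims in section 1.1 are two separate questions: "Determine the short-term effects of rTMS and rehabilitation on pain intensity" and "Determine the long-term effects of rTMS and rehabilitation on pain intensity". The hypothesis in section 1.2 is that real rTMS does better than sham. Neither aim is tied to a visit.

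On sample size, section 5.2 says: "Effect size was calculated using a 2-point NPRS change and a standard deviation of 1.7". It then takes a partial eta-squared of .07, which gives f = .274, and adds: "Sample size was calculated for 2 groups, 4 measurements, with a correlation of .5, and nonsphericity of 1". It does not say which four measurements these are. Sections 11.0 and 11.1 schedule nine: baseline, four weekly scores, and follow-up at 4 weeks, 3 months, 6 months and 1 year.

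Section 4.1 states: "Randomization will be performed in REDCap and be stratified by upper or lower extremity". The stratum does not reappear in section 5.1. On numbers, section 6.1 says "The goal is to have at least 20 subjects complete all testing", and section 2.1 says "Stage two of the study will continue until a total of 20 subjects have completed the testing, or 30 total subjects have been enrolled". Section 18.3 restricts the primary analysis to subjects who complete 80% of treatment, and mentions an analysis at 3 months.

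**The concern.** A two-way repeated-measures ANOVA yields three tests: time, group, and group by time. The aims need an arm difference at the end of treatment and another in the long term. The time effect does not compare arms. The interaction tests whether the arm difference changes over time, which is a different question from how large it is at a given time. The group effect is an arm difference, but one averaged over whatever time levels are entered.

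If the choice is left open, a significant result would still need a follow-up comparison to say when, and by how much, real rTMS beats sham. With up to eight post-baseline visits, that choice could be made after seeing the data. Baseline NPRS is collected anyway, and leaving it out as a covariate usually widens the confidence interval. With about 20 completers in a rare condition, that matters.

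**Working it through.** **Inputs.** From section 5.2: f = .274, alpha 0.05, 2 groups, m = 4 measurements, correlation ρ = 0.5, nonsphericity 1, N = 20, 2 points, SD 1.7. Assumptions of this check: the 2 points are a between-arm difference (section 5.2 says only a change); exactly 10 subjects per arm are analysed; and the correlation is the same between all visits.

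**1. Reproduce N = 20.** f = √(.07/.93) = 0.274.
- Interaction: λ = f²·N·m/(1−ρ) = 0.0753 × 20 × 4/0.5 = 12.04, with 3 and 54 df. Power is 0.81 (0.76 at N = 18), so N = 20 is reproduced.
- Time main effect: with two groups, λ and df are the same, so it also gives N = 20.
- Between-arm main effect: λ = f²·N·m/(1+(m−1)ρ) = 0.0753 × 20 × 4/2.5 = 2.41, with 1 and 18 df. Power is 0.31, and 80% would need N = 68.

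Among the tests that compare arms, only the interaction fits the stated size.

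**2. Put the tests on the same effect.** The 0.31 belongs to f = .274 and cannot be set beside a power computed from 2 points and SD 1.7. For arm differences d over m levels, the interaction has f = √(mean[((d − mean d)/2)²])/1.7 and the main effect has f = (mean d)/(2 × 1.7). The immediate course is 2 points at every weekly score. The linear course is 0.5, 1, 1.5, 2.

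| Test, 10 per arm, ρ = 0.5 | Immediate | Linear |
|---|---|---|
| Interaction, baseline + 4 weeks | 0.73 (f 0.235, λ 11.07) | 0.61 (f 0.208, λ 8.65) |
| Interaction, 4 weekly scores only | 0.05 (f 0) | 0.36 (f 0.164, λ 4.33) |
| Main effect, 4 weekly scores only | 0.88 (f 0.588, λ 11.07) | 0.50 (f 0.368, λ 4.33) |
| Main effect, baseline + 4 weeks | 0.73 (f 0.471, λ 7.38) | 0.36 (f 0.294, λ 2.88) |
| Week-4 ANCOVA | 0.79 | 0.79 |
| Week 4, unadjusted | 0.70 | 0.70 |
| Four-week-mean ANCOVA | 0.97 | 0.69 |

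Depending on the term, the time levels and the course, the planned ANOVA has power anywhere from 0.05 to 0.88 for the same 2-point benefit.

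**3. The single-visit contrast.**
- Unadjusted: SE = 1.7 × √(2/10) = 0.760, and 2/0.760 = 2.63 on 18 df, so power is 0.70. The mean simulated 95% CI half-width is 1.58.
- Adjusted: residual SD = 1.7 × √(1 − 0.5²) = 1.47, SE = 0.658, and 2/0.658 = 3.04 on 17 df, so power is 0.82 by formula. Simulation with chance baseline imbalance and the stratum term gives about 0.79 and a half-width of 1.42. The lower figure is used here.
- Sensitivity to ρ: at 0.3 the adjusted and unadjusted powers are 0.71 and 0.70. At 0.7 they are 0.92 and 0.70.

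**4. Does the interaction answer the aims?**
- Short term, baseline + 4 weeks, differences 0, 2, 2, 0, 0: f = 0.288, λ = 16.6, and it rejects in 90% of trials. The week-4 difference is zero, and week-4 ANCOVA rejects in 5%.
- Long term, all nine times. Fading effect (0, 2, 2, 2, 2, 1, 0, 0, 0): it rejects in 98%. Sustained 2 points at all eight post-baseline times: f = 0.185, λ = 12.3 on 8 and 144 df, and it rejects in 67%. The 1-year ANCOVA gives 5% and 79%.

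**The case against.** The documents never use the word interaction. Section 5.2 refers to between and within comparisons, and the time main effect also gives N = 20. A reader might infer that the plan openly commits to the interaction. It does not: the sample size is only consistent with it.

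A reader might also infer that the plan contains no arm comparison, or that its arm comparison always has 31% power. Neither follows. Section 5.1 includes a between effect, and section 11.0 counts four end-of-week measurements, which matches the four in section 5.2. On that reading the between effect is the mean arm difference over the four weekly scores. With an immediate 2-point effect its power is 0.88, above the 0.79 of week-4 ANCOVA. This objection stands, and it limits the power argument. It does not settle which term decides, and on that same reading the interaction has 5% power for a constant benefit.

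Nor are analyses by time point wholly unplanned. Section 18.3 foresees one at 3 months, but no arm contrast is defined for it.

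The gain from baseline adjustment depends on the correlation and is close to nil at 0.3. ANCOVA does not always win: at correlation 0.7 with an immediate effect, the interaction (baseline as a level) has 0.93 against 0.92. With 15 per arm, which the limit of 30 enrolled allows only without dropout, the interaction reaches 0.82 (linear) or 0.91 (immediate). The weeks-1-2 case is an extreme, chosen to show what the test responds to.

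**Conclusion.** The point holds as a mismatch between test and aim. The plan does not say what decides either aim, and the test its sample size fits can be positive when the difference asked about is zero (90% in the short-term example). In the nine-visit examples it favours a fading effect over a lasting one (98% against 67%). The between effect is a legitimate arm comparison, but its power and meaning depend on unstated time levels and on the course of the effect, and entering baseline as a level dilutes it (0.88 to 0.73 if immediate, 0.50 to 0.36 if linear).

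The power gain is secondary: about 0.79 against 0.70 at week 4, with the half-width falling from 1.58 to 1.42 points. It rests on a 2-point arm difference, SD 1.7, correlation 0.5 and 10 per arm. The documents do not support calling the ANOVA invalid, and nothing here shows that the sample size must rise. The change should be made before unblinding.

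**What to change.** In section 5.1:
- Make the primary test one short-term arm contrast: week 4, or the mean of the four weekly scores. Estimate it by ANCOVA adjusted for baseline NPRS and extremity, with a 95% CI. Extremity belongs in the model because randomisation is stratified by it, not because a power gain has been shown.
- Name one long-term contrast, for example at 1 year. Call it secondary, or test it only after the short-term contrast succeeds, so that alpha is not split. By formula, with baseline as the only covariate, splitting to 0.025 each would leave 71.5% power at 10 per arm instead of 81.7%.
- Estimate the long-term contrast by baseline-adjusted ANCOVA at that visit, with a mixed model as support.
- State how both analyses fit the 80%-completion rule in section 18.3.

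**Cost.** Wording only, no new data. Two residual degrees of freedom are used (16 remain of 18), and the stratum term costs about 0.003-0.005 of power if extremity does not predict pain. Week 4 is weaker than the four-week mean if the effect is immediate (0.79 against 0.97) and stronger if it builds slowly (0.79 against 0.69), so the choice should follow the expected course.

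Neither long-term method is free of risk. In simulation the 1-year ANCOVA was biased by 0.2-0.5 points when only sham subjects with more pain dropped out (mixed model 0.0-0.1). A compound-symmetry mixed model had a false-positive rate of 0.09-0.12 when correlation decays with time. A small-sample correction such as Kenward-Roger may help but was not tested, which is why the mixed model is proposed only as support.

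### Plain logistic regression for 30% responders and PASS may give no finite odds ratio at about 10 subjects per arm, depending on an unstated sham rate; a penalised model at named visits is a cheap improvement

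*Combined protocol and SAP*

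**What the plan says.** Section 5.1 lists two binary secondary outcomes. For pain response it gives "NPRS number reaching 30% improvement: Descriptive (%), Logistic Regression", and for the acceptable-symptom question "PASS: Logistic Regression". It names no estimator, time point, covariates, rule for empty cells or method for repeated answers.

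The sample size in Section 5.2 was derived for a repeated measures ANOVA, not for these models: "This resulted in a group size of 10 participants for a total of 20 subjects". Section 6.1 makes that number a target: "The goal is to have at least 20 subjects complete all testing". The enrolment ceiling is higher but differs between sections: "a maximum of 33 subjects will be enrolled in the study" (6.1), "To account for dropouts up to 36 subjects will be enrolled in this study" (5.2), and 30 in Section 2.1.

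Sections 11.0 and 11.1 collect both outcomes at four weekly visits and four later follow-ups (4 weeks, 3 months, 6 months, 1 year), so there are eight post-baseline occasions. Section 4.1 stratifies randomisation by upper or lower extremity.

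**The concern.** Ordinary logistic regression estimates the odds ratio by maximum likelihood. When one arm contains only responders or only non-responders, the likelihood keeps rising as the coefficient goes to infinity. Software then prints a huge odds ratio with a meaningless standard error, or a convergence warning. With ten subjects in an arm this is not remote if the response rate there is low. The table most likely to break the model, several responders on real rTMS and none on sham, is also the one most favourable to the treatment.

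Two further matters follow. Wald tests and intervals, the default output, behave poorly at this size. And with eight answers per subject and no stated time point, an analyst could stack all answers in one ordinary logistic model, which would count one person's correlated answers as independent. If these choices are left until the data are seen, the model may be picked because the first attempt failed.

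**Working it through.** **The plan's own figure.** Section 5.2 uses partial eta squared 0.07, two groups, four measurements, correlation 0.5, nonsphericity 1 and alpha 0.05, and "power was set at 80"%.

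- f = sqrt(0.07/0.93) = 0.274, as stated.
- Noncentrality = f² × N × m/(1 − ρ) = 0.274² × 20 × 4/0.5 = 12.0, on 3 and 3 × (20 − 2) = 54 degrees of freedom.
- Power is 0.811 at N = 20 and 0.759 at N = 18, so 20 in total (10 per group) is reproduced.

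**Inputs for the binary outcomes.** n = 10 per arm is the completer target. The only response rate in the documents is 51-70% in Section 3.1, from earlier rTMS studies. It counts subjects with pain relief, not a 30% NPRS improvement, so using it for the real arm is an assumption. The sham rate is not given and is varied from 5% to 40%. No PASS rate is given for either arm; for PASS, read the table as showing what such rates would imply.

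**Chance of no finite odds ratio (arm-only model).** With real-arm rate p and sham rate s:

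P = 1 − [1 − pⁿ − (1 − p)ⁿ] × [1 − sⁿ − (1 − s)ⁿ]

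For p = 0.51, s = 0.20, n = 10: 0.51¹⁰ + 0.49¹⁰ = 0.0020 and 0.20¹⁰ + 0.80¹⁰ = 0.1074, so P = 1 − 0.9980 × 0.8926 = 0.109.

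| Assumed sham rate | 10 per arm, real 51% | 10 per arm, real 70% | 15 per arm, real 51% | 15 per arm, real 70% |
|---|---|---|---|---|
| 5% | 60% | 61% | 46% | 47% |
| 10% | 35% | 37% | 21% | 21% |
| 20% | 11% | 13% | 3.5% | 4.0% |
| 30% | 3.0% | 5.6% | 0.5% | 0.9% |
| 40% | 0.8% | 3.4% | 0.1% | 0.5% |

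Adding the extremity stratum to an unpenalised model raises the 10-per-arm risk. By simulation, with an assumed 6/4 split in each arm, it is about 16-21% at a 20% sham rate and 39-44% at 10%.

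**Test behaviour at 10 per arm.** Full enumeration of the 2×2 tables, nominal 5%, arm-only model, with Wald counted as non-significant when a cell is empty:

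| True rates | Firth likelihood ratio | Wald | Fisher |
|---|---|---|---|
| 10% v 10% | 0.9% | 0.0% | 0.1% |
| 20% v 20% | 3.0% | 0.4% | 0.8% |
| 30% v 30% | 3.7% | 1.7% | 1.2% |
| 50% v 20% | 25% | 16% | 13% |
| 70% v 20% | 62% | 49% | 43% |

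The Firth test stays below 5% and rejects more often than the other two when the arms differ.

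**An empty cell under the remedy.** Take 5/10 v 0/10. In the arm-only model, Firth's penalty adds 0.5 to each cell, so OR = (5.5 × 10.5)/(5.5 × 0.5) = 21, which is finite. For the risk difference of 0.50, the Wilson limits are 0.237 to 0.763 for 5/10 and 0 to 0.278 for 0/10. Newcombe's interval runs from 0.50 − sqrt(0.263² + 0.278²) = 0.12 to 0.50 + sqrt(0.263² + 0²) = 0.76.

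**If occasions were pooled as independent.** By simulation at 10 per arm (assumed 30% responders in both arms, latent within-subject correlation 0.3 to 0.7), the type I error is about 11-21% with four visits and 19-35% with eight, against 5%.

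**The case against.** The separation risk depends on a rate that nobody has stated. The sham arm receives active rehabilitation, and Section 20.1 says this could improve symptoms. At sham rates of 30% or more the problem largely disappears. This stands, and is why no single probability should be quoted. It does not settle the matter, because Section 3.1 describes first-line care, including graded motor imagery, as having small effects, so a low sham rate is also credible.

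Ten per arm may be exceeded at week 4. The target of 20 refers to subjects who finish all testing, including one year, and Section 18.3 keeps later dropouts in earlier analyses. This also stands, and the 15-per-arm columns show the gain. But Section 2.1 ends stage two once 20 have completed, so 10 is a fair planning figure. If the target were missed and 8 per arm remained, the risk would be about 17-22% at a 20% sham rate.

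A reader might infer that the plan ignores the correlation between repeated answers. The documents do not support that. Section 5.1 is silent, and the example in Section 18.3, where subjects who reach 3 months enter that visit's analysis, points to separate analyses by visit, which involve no pooling. By-visit fitting has its own cost: two outcomes at eight occasions make up to 16 fits, and the chance that at least one is inestimable is no lower than for one fit.

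Finally, percentages for 30% responders are already planned, so an infinite odds ratio would not leave that outcome unreported. That limits the harm. PASS has no such descriptive line.

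**Conclusion.** The point holds as a cheap improvement to two secondary analyses. At 10 per arm, with 51-70% response assumed on real rTMS, the chance of no finite odds ratio runs from about 1% (sham 40%) to about 60% (sham 5%), and is 11-13% at a 20% sham rate. At 15 per arm and a 20% sham rate it is about 4%. These figures rest on an assumed sham rate and on a real-arm rate borrowed from a differently defined outcome; for PASS they are illustrative only.

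The unpenalised Wald test is also too conservative at low response rates. The handling of repeated answers is unspecified rather than shown to be wrong; pooling is a risk to close off, not an error in the text. Nothing here touches the primary NPRS analysis.

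**What to change.** In Section 5.1, for each of the two outcomes:

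- Fit Firth-penalised logistic regression on arm and extremity stratum, with profile-likelihood confidence intervals and a penalised likelihood ratio test.
- Do this at week 4 for the short-term aim and at one follow-up visit, named in advance, for the long-term aim. Week 4 alone would leave the second aim in Section 1.1 without an analysis of these outcomes.
- Report the number and percentage responding in each arm, and the risk difference with a Newcombe interval.
- State that occasions will not be pooled unless the model has a within-subject term.

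The cost is a few lines of text and standard software; no extra data or subjects are needed. The odds ratio is shrunk slightly towards 1. The change makes the estimate usable but does not make these outcomes well powered: about 25% at 50% v 20% with 10 per arm. They should be reported as estimates with intervals, and a non-significant result should not be read as evidence of no effect.

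### Section 5.2 labels the powered effect as partial η² = .07, but N = 20 gives 80% power only if f = .274 is a pre-correlation effect size, which is a partial η² of about .17–.18 in the planned ANOVA

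*Combined protocol and SAP*

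**What the plan says.** Section 5.1 of the combined protocol and SAP sets the primary analysis: "Primary: NPRS weekly average: 2-way ANOVA for within and between effects".

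Section 5.2 gives the only sample-size justification:

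- Software and test: "G*Power 3.1.9.7 was used to calculate the sample size based on a repeated measures ANOVA with between and within measures comparisons".
- Clinical basis: "Effect size was calculated using a 2-point NPRS change and a standard deviation of 1.7".
- Effect size entered: "A partial η^2 of .07 (moderate effect size) gave an effect size of .274", with α = 0.05 and a power target of 80%.
- Design inputs: "Sample size was calculated for 2 groups, 4 measurements, with a correlation of .5, and nonsphericity of 1".
- Result: "This resulted in a group size of 10 participants for a total of 20 subjects".

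Section 5.2 does not say which effect was powered (interaction, within or between). It does not define the scale of the effect size or show how 2 points and an SD of 1.7 lead to .07. Section 6.1 then rests enrolment on this power analysis and aims for at least 20 subjects completing all testing.

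**The concern.** In a repeated measures ANOVA, the partial η² of a group-by-time term is SS_effect/(SS_effect + SS_error), where the error is the within-subject one. That error is already reduced by the correlation between a subject's repeated ratings. If .07 is such a value, converting it to f and then entering the correlation of .5 credits that correlation twice.

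The other possibility is that f = .274 is the SD of the effects divided by the raw within-cell SD. The correlation is then properly entered once, but the effect will not appear as a partial η² of .07 in the ANOVA that Section 5.1 specifies.

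Interpretation is at stake. The primary analysis belongs to the ANOVA family in which partial η² is commonly reported, so a reader will compare the reported value with .07. That reader would believe the trial had 80% power for an effect of that size.

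**Working it through.** **Inputs, all from Section 5.2.** Partial η² = .07, f = .274, α = .05, k = 2 groups, m = 4 measurements, ρ = .5, nonsphericity ε = 1, N = 20. Power comes from the noncentral F distribution. For the group-by-time interaction, df1 = (k − 1)(m − 1) = 3 and df2 = (N − k)(m − 1) = 18 × 3 = 54.

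**Step 1. The conversion.** f = √(.07/.93) = √.0753 = .2744. This agrees with the stated .274.

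**Step 2. Reproduce N = 20.** Treat f as a pre-correlation effect size:

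λ = f² × N × m/(1 − ρ) = .0751 × 20 × 8 = 12.0

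- N = 20: power 81.1%.
- N = 18: λ = .0751 × 18 × 8 = 10.8, power 75.9%.

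So 20 is the smallest even total that reaches 80%. A simulation of 20,000 trials with this effect gave 81.4%. The within-subject main effect has the same df and λ, so N alone cannot separate it from the interaction. The between-group main effect can be ruled out: λ = .0751 × 20 × 4/(1 + 3 × .5) = 2.40 on 1 and 18 df gives 31% power.

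**Step 3. Express that effect as an ANOVA partial η².**

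- With λ = [η²/(1 − η²)] × (N − k)(m − 1): η² = 12.0/(12.0 + 54) = .18.
- With λ = [η²/(1 − η²)] × N(m − 1): η² = 12.0/(12.0 + 60) = .17.

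**Step 4. Take .07 as the ANOVA partial η².** The correlation is already in the error term, so the factor of 8 is not applied.

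| Noncentrality | λ at N = 20 | Power at N = 20 | Smallest even N for 80% |
|---|---|---|---|
| .0753 × (N − k)(m − 1) | .0753 × 54 = 4.06 | 34.0% | 52 (80.4%) |
| .0753 × N(m − 1) | .0753 × 60 = 4.52 | 37.5% | 50 (80.3%) |

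Simulation of the first row gave about 35%. Analysing everyone at the stated enrolment caps, 33 (Section 6.1) or 36 (Section 5.2), would give about 57–64% across the two forms.

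**Step 5. What the 2-point target implies.** The plan gives no trajectory, so these patterns are assumptions. Each row is the between-group divergence in NPRS points over four occasions with SD 1.7. f is the SD of the interaction effects divided by 1.7, and λ = f² × 160.

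| Divergence | f | f²/(1 + f²) | Power at N = 20 |
|---|---|---|---|
| 0, .67, 1.33, 2 | .219 | .046 | 60% |
| 0, 1, 2, 2 | .244 | .056 | 70% |
| 0, 2, 2, 2 | .255 | .061 | 74% |
| 0, 0, 2, 2 | .294 | .080 | 87% |

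As a simple two-group contrast the same inputs give d = 2/1.7 = 1.18, f = .59 and η² = .59²/(1 + .59²) = .26, which is not .07.

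**The case against.** The strongest reply is that nothing was miscalculated. Every stated input reproduces N = 20, which shows that f = .274 was used on the scale where the correlation is entered separately. On that scale f²/(1 + f²) is .07 by definition, and the correlation is applied once. Section 5.2 cites no ANOVA table from which .07 was taken. It does refer to a 2-point change and to SDs of pain ratings, which are raw-scale quantities. The assumed trajectories in Step 5 give .046 to .080 on that scale, a range that includes .07.

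Most of this stands. The total of 20 is sound for f = .274 on the raw-SD scale, and calling that effect moderate is then defensible. The stated N shows which scale was used; it does not prove that the sponsor counted the correlation twice.

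A reader might go further and infer that the trial has only 34% power for its clinical target, or that N must rise to 50–52. The documents do not support either inference. The 34–38% belongs to an ANOVA partial η² of .07, not to a 2-point difference, for which power is about 60–87% under the assumed patterns.

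The reply does not rescue the label. If f was meant on the raw-SD scale, the effect is not a partial η² of .07 in the planned ANOVA. If .07 was meant as the ANOVA quantity, 80% power does not hold. Under either reading, one of the two statements has to change.

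**Conclusion.** The point holds as a mismatch between the stated power and the stated effect label. Twenty completers give about 81% power for f = .274 defined before the correlation is applied. That equals a partial η² of about .17–.18 in the planned ANOVA, roughly two and a half times the stated .07 (.18/.07 = 2.6; .17/.07 = 2.4). A true ANOVA partial η² of .07 would have about 34–38% power.

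These figures assume the group-by-time interaction, 4 measurements, a correlation of .5, sphericity and 20 analysed subjects. The ranges reflect two conventions for the noncentrality. The scale used is inferred from N = 20, because Section 5.2 does not name it. The randomised comparison itself is unaffected. How .07 was obtained from 2 points and an SD of 1.7 is left unexplained, and only the sponsor can settle it.

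**What to change.** Keep N and restate the effect-size sentences in Section 5.2 along these lines:

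> 20 completers give about 81% power for a group-by-time interaction of f = .274, defined on the raw within-cell SD before applying the correlation of .5 (4 measurements, sphericity). This is equivalent to a partial η² of about .17–.18 in the planned ANOVA. If .07 is meant as the ANOVA partial η², power is about 34–38%.

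The last sentence can be dropped once the sponsor confirms that the raw-SD scale was meant. In the same edit:

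- remove the unqualified partial η² of .07;
- keep the word moderate only if it is tied to the raw-SD f;
- confirm that the interaction, rather than the within-subject main effect, is the effect powered;
- state the assumed trajectory that links the 2-point change and SD 1.7 to f.

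The cost is one paragraph of wording. No extra patients and no design change are needed.
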